
mini-vaccination stations in communities highly impacted by the pandemic and identifying individual and structural barriers to COVID-19 immunization (Phase 2). Specific aims include:

Aim 1. To evaluate the preliminary impact of 2VIDA! compared to the standard-of-care for COVID-19 vaccination services among Latinx and AA adults ≥ 16 years (N=1000) in San Diego. We will use a 2-armed randomized controlled trial (RCT)* where Latinx and AA adults ≥ 16 years or older from six participating community health centers (CHC) and surrounding communities will be assigned to the 2VIDA! intervention (n=3 CHC; N=500 participants) or to the control site (e.g., standard of care) (n=3 CHC; N=500 participants). Data will be collected on a) sociodemographic characteristics; b) characteristics associated with social marginalization; c) access to and utilization of health care; d) vaccination history, interest, hesitancy and uptake; e) perceptions of the COVID-19 vaccine (e.g., fears, myths, etc.); f) general health; and h) trust in government, research, and social agencies, i) satisfaction with 2VIDA!; at baseline and 4-week follow-up. We hypothesize that at follow-up, compared to control participants, 2VIDA! participants will:

H.1. have increased knowledge about the COVID-19 vaccine (including medically accurate information, benefits, and risks);
H.2. more likely to receive the COVID-19 vaccine;
H.3. more likely to complete vaccine series (based on Centers for Disease Control and Prevention [CDC] recommendations).¹

Aim 2. To assess feasibility, acceptability, and intervention effects of 2VIDA! To assess feasibility and acceptability, we will utilize quantitative methods to track recruitment, condition assignment, participant retention, intervention implementation, and potential threats (e.g., contamination). We will also utilize qualitative methods to assess acceptability via focus groups with participants to understand potential for broad implementation (e.g., what components did they receive of the intervention, client satisfaction, linkage to COVID-19 services). To assess intervention effects, we will examine participant vaccination rates/completion across both groups.

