*Please note that only one community health center out of their 25 clinics is currently delivering 2VIDA! as a clinical program and all of their clinics are offering the vaccine on site (no mini-vaccination stations). For the purposes of this research, we will randomize 6 community health centers and their surrounding communities that are predominantly Latinx and AA to receive either 2VIDA! or the standard of care for vaccine delivery (i.e. no components of 2VIDA! will be deployed). In order to avoid contamination, the community health center where the 2VIDA! was developed (i.e., Chula Vista) and is currently being implemented as a clinical program will be excluded from this study. Additionally, SYH is currently offering the vaccine at their community health centers, however, there is low vaccine uptake, therefore we believe this study will help increase interest in the vaccine and address vaccine hesitancy by working with the community.

6. BACKGROUND AND SIGNIFICANCE (2-3 paragraphs maximum)

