Focus Groups (FG). Two separate FGs (one in English and one in Spanish) will be conducted (n=2; 8-10 participants per group) following the implementation of *2VIDA!* with members of the Latinx and AA community in San Diego to understand the socio-structural barriers to COVID-19 information and resources (e.g., testing) and vaccine uptake (e.g., medical mistrust, discrimination, stigma, transportation, access to vaccination site, lack of insurance) as well as acceptability of the *2VIDA!* intervention. Participants will be recruited from six SYH community health centers (from both intervention and control sites) that are located in the communities with the highest cases of COVID-19. Eligibility criteria includes: 1) identify as Latinx or African American, 2) 16 years of age or older, 3) reside in one of the target communities (National City, Lincoln Park, Logan Heights, Valencia Park, San Ysidro), 4) literate in English or Spanish, 5) able to provide written and informed consent (including permission to record FG session). We will recruit equal number of Latinx and AA participants for each session, as well as equal number of individuals who both have and haven't received the vaccine as part of *2VIDA!* to provide an in-depth discussion and have a better understanding of the community needs. The FGs will take place based on the time/date that is most convenient for the community members. Each FG will take place in the private conference room located in the clinics, will follow a semi-structured open-ended guide, last between 60-90 minutes and be facilitated by a moderator ([name]) and note-taker (who also records each session). This data will allow us to identify structural barriers, acceptability, and feasibility of *2VIDA!* on COVID-19 vaccination uptake.

Data Analysis. We will approach overall data analyses using a multivariate repeated measures design (i.e., doubly multivariate) to assess mean differences in treatment and control groups on our primary (acceptance of COVID-19 vaccine and vaccine series completion) and secondary outcome variables (increased knowledge of COVID-19 vaccine, increased

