access to COVID-19 vaccine, vaccine hesitancy). Additional measures at baseline and follow-up will be used as covariates (e.g., outreach and health communication, vaccine hesitancy or mistrust). Mean differences, both within and between treatment and control groups as well as group by treatment interaction effects will be analyzed. The targeted sample size is sufficient to detect a small effect size (.20) with power = .90 at alpha = .05 accounting for moderate participant attrition.

Descriptive Statistics. To describe the overall sample regarding demographics, structural and individual barriers, and potential covariates of intervention effects at baseline, prevalence statistics and means and standard deviation will be provided for all baseline variables; Cronbach's alpha of .70 will be required to be considered reliable. **Baseline Analyses to Detect Differences Between Treatment Groups.** Chi-square analyses and paired t-tests will be used to detect differences in demographics, knowledge of COVID-19 vaccine, access to COVID-19 vaccine, acceptance of COVID-19 vaccine and series completion, COVID-19 resource-seeking behaviors and linkage into care between intervention and control groups. Demographic variables included in these analyses will be age, gender, race/ethnicity, education, household income, marital status, and having insurance. Those variables differing across treatment groups at the $p < .20$ level will be included in subsequent adjusted outcome analyses. For the qualitative data analysis, final translated electronic transcripts will be imported into Dedoose. Analysis will be done through identification of recurrent themes following Crabtree and Miller's 5 step "interpretive process."¹⁹ First, transcripts will be read to identify common themes, codes will be developed and ~10% of data will be double coded and inter-rate reliability assessed. Coded text will be extracted and organized and read to identify emergent themes.⁶⁵ Matrices will be created to compare codes by themes (e.g., medical mistrust, discrimination, stigma, transportation, access to vaccination site, lack of insurance). Data will be utilized to refine *2VIDA!*, assess acceptability, and inform future vaccination efforts among underserved communities.

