10. RECRUITMENT

Six SYHealth community health centers across San Diego County have been selected based on their serving predominantly Latinx and AA client population and having the Zip codes with the highest number of COVID-19 cases in the County. These clinics are located in National City, Logan Heights, Lincoln Park, Valencia Park and San Ysidro. Each clinic will be randomly selected and randomized evenly to either the intervention or control conditions, using computer-generated randomization plans prepared using SAS statistical software under the direction of the lead study statistician. Clinic-level randomization was selected to minimize between-arm contamination of intervention and control conditions. Participants from both intervention (n=500) and control sites (n=500) will be recruited using reactive recruitment, including the use of community partner social media platforms, and flyers distributed in the SYH target health centers and high traffic, readily visible areas, where eligible participants are likely to see them (e.g., grocery stores, local CBO's, parks, barber shop, cafés, food banks, gyms, local restaurants). Flyers will include study information and contact information for study staff. Likewise, the project staff publicized the rapid vaccine effort (e.g., mini-vaccination stations) by posting flyers that noted locations, dates, and times of vaccine distribution, and through presentations about the project at community meetings. Project staffing, training, and support, including the selection of nurses and outreach staff (e.g., peer-health educators and research assistants) with complementary research skills and personal knowledge of the community will be key to the success of the project. Two bilingual Latinx (one male and one female) and two AA (one male and one female) outreach workers trained in research ethics and protocols, and familiar with this population will approach individuals who appear to be eligible (Latinx and AA adults ages 16 years or older) at the SYH community centers and mini-vaccination stations in the participating communities, confirm eligibility, and describe the study to those eligible. Research staff will update time logs and continuously update our sampling frame until recruitment is finalized. The reason for refusal or ineligibility will be recorded. Extensive efforts will be made to have an equal representation of Latinx and Black community members and at least 40% women.

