Cover Page for ClinicalTrials.gov

Document: Statistical Analysis Plan

Official Study Title: Project 2VIDA! COVID-19 Vaccine Intervention Delivery for Adults in Southern California

NCT number: NCT05022472

Document date: February 5, 2021

STATISTICAL DESIGN AND POWER CALCULATIONS

We will approach overall data analyses using a multivariate repeated measures design (i.e., doubly multivariate) to assess mean differences in treatment and control groups on our primary (acceptance of COVID-19 vaccine and vaccine series completion) and secondary outcome variables (increased knowledge of COVID-19 vaccine, increased access to COVID-19 vaccine, vaccine hesitancy). Additional measures at baseline and follow-up will be used as covariates (e.g., outreach and health communication, vaccine hesitancy or mistrust). Mean differences, both within and between treatment and control groups as well as group by treatment interaction effects will be analyzed. The targeted sample size is sufficient to detect a small effect size (.20) with power = .90 at alpha = .05 accounting for moderate participant attrition. Descriptive Statistics. To describe the overall sample regarding demographics, structural and individual barriers, and potential covariates of intervention effects at baseline, prevalence statistics and means and standard deviation will be provided for all baseline variables; Cronbach's alpha of .70 will be required to be considered reliable. Baseline Analyses to Detect Differences Between Treatment Groups. Chi-square analyses and paired t-tests will be used to detect differences in demographics, knowledge of COVID-19 vaccine, access to COVID-19 vaccine, acceptance of COVID-19 vaccine and series completion, COVID-19 resource-seeking behaviors and linkage into care between intervention and control groups. Demographic variables included in these analyses will be age, gender, race/ethnicity, household income, marital status, and having insurance. Those variables differing across treatment groups at the $p < .20$ level will be included in subsequent adjusted outcome analyses.

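### Six clinics are randomised (3 vs 3), but the analysis and the .90 power statement treat participants as independent

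*SAP*

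**What the plan says.** **Unit of randomisation.** The Protocol is clear that clinics are randomised. The footnote to Section 5 (Specific Aims), repeated at the end of Section 8, states that "we will randomize 6 community health centers and their surrounding communities that are predominantly Latinx and AA". Section 10 (Recruitment) adds that "Each clinic will be randomly selected and randomized evenly to either the intervention or control conditions", and gives the reason: "Clinic-level randomization was selected to minimize between-arm contamination of intervention and control conditions". Aim 1 sets the sizes: the "intervention (n=3 CHC; N=500 participants) or to the control site (e.g., standard of care) (n=3 CHC; N=500 participants").

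**Analysis.** The SAP and the Data Analysis paragraph of Protocol Section 8 share the same core text. The arms are compared by a "multivariate repeated measures design (i.e., doubly multivariate) to assess mean differences in treatment and control groups on our primary" and secondary outcomes. The Protocol continues: "Mean differences, both within and between treatment and control groups as well as group by treatment interaction effects will be analyzed". The adjusters are survey measures and baseline variables that differ between arms at p < .20. Clinic is not among them. Neither document mentions a random effect, cluster-robust variance, ICC, design effect or clinic-level degrees of freedom.

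**Power.** The sample size is said to be "sufficient to detect a small effect size (.20) with power = .90 at alpha = .05 accounting for moderate participant attrition". No attrition rate, baseline correlation or ICC is given.

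**The concern.** A repeated measures model handles the correlation between two visits by one person. It does not handle the correlation among people at the same clinic. 2VIDA! acts largely at site level, through resource centers, park stations and community outreach, so arm is confounded with whatever else distinguishes one set of three clinics from the other.

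If outcomes within a clinic are positively correlated, 1,000 participants carry less information about the arm difference than the model assumes. The result is false positives and overprecise intervals for H.1 to H.3.

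A change score removes the problem only where a clinic's effect is identical at both visits. It gives no protection for H.2 and H.3 (vaccine receipt and series completion) if nobody has the outcome at baseline. Under Phase II of Section 8 the vaccine is offered after the baseline survey, so uptake through the study is a follow-up outcome.

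**Working it through.** **Inputs from the documents:** 3 clinics and n = 500 participants per arm; effect size .20 (read as a standardised mean difference); alpha .05 (taken as two-sided); stated power .90.

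**Assumed, because not given:** equal clinics, m = 500/3 ≈ 167; ICC 0 to 0.02; attrition 0 to 20%; baseline correlation r = 0, 0.5 or 0.7.

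**1. The stated .90, with independent participants.** Noncentral t, 2n − 2 df, noncentrality 0.20/√(2(1 − r²)/n):

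| n per arm (loss) | r = 0 | r = 0.5 |
|---|---|---|
| 500 (0%) | 0.885 | 0.954 |
| 450 (10%) | 0.850 | 0.933 |
| 400 (20%) | 0.807 | 0.904 |

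So .90 can be reached at participant level with an unstated baseline correlation, but only with no clustering.

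**2. True type I error of the participant-level test.** Design effect DE = 1 + (m − 1) × ICC. Error = 2(1 − Φ(1.96/√DE)). At ICC 0.01, DE = 1 + 165.7 × 0.01 = 2.66 and 1.96/√2.66 = 1.20, which gives 22.9%.

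| ICC of tested quantity | 0.001 | 0.005 | 0.01 | 0.02 |
|---|---|---|---|---|
| DE | 1.17 | 1.83 | 2.66 | 4.31 |
| Error, equal clinics | 6.9% | 14.7% | 22.9% | 34.5% |
| Error, 20% loss (m = 400/3) | 6.5% | 12.8% | 19.8% | 30.5% |
| Error, clinics of 300, 125 and 75 per arm | 7.6% | 17.7% | 27.4% | 40.0% |

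The last row uses DE = 1 + (Σm²/n − 1) × ICC, with Σm²/n = 222.5. A simulation of 40,000 trials with 167 per clinic gave 7.0, 14.6, 23.2 and 34.6% for the participant-level test of the follow-up outcome, and 4.8 to 5.2% for a clinic-level t-test on 4 df.

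**3. Change scores.** With clinic effects correlated rc over time and participant effects correlated rp, the ICC of the change is ICC(1 − rc)/[ICC(1 − rc) + (1 − ICC)(1 − rp)]. With rc = 0.9 and rp = 0.5, outcome ICCs of 0.005, 0.01 and 0.02 become 0.0010, 0.0020 and 0.0041, and the error is 7.0, 9.0 and 13.0%. With rc = 1 it is 5.0%.

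**4. Power of a clinic-level test.** Noncentral t on 2 × 3 − 2 = 4 df, noncentrality 0.20/√(2(1 − r²)DE/n). Where r > 0, the ICC is that of the adjusted outcome.

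| Setting | ICC 0 | 0.001 | 0.005 | 0.01 | 0.02 |
|---|---|---|---|---|---|
| No loss, r = 0 | 66% | 60% | 43% | 32% | 22% |
| No loss, r = 0.5 | 78% | 72% | 54% | 40% | 27% |
| No loss, r = 0.7 | 90% | 86% | 69% | 54% | 37% |
| 10% loss, r = 0.7 | 87% | 83% | 67% | 52% | 37% |
| 20% loss, r = 0.7 | 84% | 79% | 64% | 51% | 36% |

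**5. Interval width for an outcome near 50%, r = 0.** Participant-level: 1.96 × √(0.25 × 2/500) = 6.2 percentage points. Clinic-level: 2.776 × √(0.25 × 2 × DE/500) = 9.5, 11.9, 14.3 and 18.2 points at ICC 0.001, 0.005, 0.01 and 0.02.

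**6. More participants or more clinics.** With unlimited participants in the same six clinics, power without baseline adjustment cannot exceed 74%, 46% and 27% at ICC 0.005, 0.01 and 0.02. At 167 per clinic, 90% power needs about 5, 7, 10 and 15 clinics per arm at ICC 0.001, 0.005, 0.01 and 0.02.

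**The case against.** The strongest reply is that the .90 is not an arithmetic error. The plan uses baseline measures, and with r = 0.5 the participant-level calculation gives 0.904 at 20% loss. That stands: the defect is the missing clustering. The clinic-level shortfall also depends on where the range of r stops. At r = 0.8 and ICC 0.001, power on 4 df is 92.9% with 10% loss and 90.4% with 20% loss. By ICC 0.005 it is down to 80.5% and 77.9%.

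A second reply is that every size here is assumed, that covariate adjustment might lower the ICC, and that stable clinic effects cancel in change scores. This too is fair. It limits what can be said about size, not direction, and cancellation does not help an outcome that nobody has at baseline.

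A third is that Aim 1 seeks only preliminary impact. That bears on how strongly the result is read. It does not justify a test at alpha .05 with stated power .90 that ignores the unit randomised, and Section 16 expects the results to inform local and national scale-up.

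Finally, Aim 1 and Section 8 speak of adults being assigned, which could suggest individual randomisation. The footnotes to both sections and Section 10 rule that out.

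**Conclusion.** The concern holds and must be fixed. The planned analysis does not respect the unit of randomisation, and the documents do not support the stated power for the design they describe.

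The direction is certain for any positive ICC in the tested quantity. The size is conditional: for a follow-up outcome with equal clinics and no loss, the true error rate runs from about 7% at ICC 0.001 to 35% at 0.02. It is lower for change scores with stable clinic effects, and higher if clinics differ much in size. With 10 to 20% loss and r up to 0.7, a clinic-level test on 4 df does not reach .90 at any ICC examined, including zero.

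**What to change.** Amend the SAP and the Data Analysis paragraph of Protocol Section 8 as follows.

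1. **Make the randomised clinic the unit of inference for H.1 to H.3, and pre-specify one primary method.** The simpler choice is a two-stage analysis: clinic proportions or means adjusted for pre-specified participant covariates, then a 3 vs 3 t-test on 4 df. The alternative is a mixed model with a clinic random intercept and a named small-sample df method, with a logit link for yes/no outcomes and a stated standardisation step to obtain risk differences. The choice of df method matters, because the clinic variance will often be estimated as zero with six clinics, and fixed 4 df is then conservative. Report risk or mean differences with 95% intervals and the ICC.
2. **Rule out two alternatives.** Clinic cannot be a fixed effect, because it is nested in arm. A permutation test should not be relied on: there are C(6,3) = 20 allocations, so its smallest two-sided p is 2/20 = 0.10.
3. **Keep each participant's randomised clinic in the analysis data.** Section 14 says enrolment also takes place at the mini-stations. Section 8 says the stations support the centers but does not link each one to a clinic. The sponsor should record that link in advance and analyse station enrolees under the linked intervention clinic.
4. **Replace the power sentence** with clinic-level power over stated ranges of ICC, attrition and baseline correlation. Say plainly that six clinics limit the trial to preliminary evidence.

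The cost is revised wording, different analysis code and one clinic variable. The price is wider intervals and a much lower stated power. Enrolling more people at the same six clinics would not remove that limit; only more clinics would.

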PHASE II. To evaluate the preliminary impact of 2VIDA! compared to the standard-of-care for COVID-19 vaccination services among Latinx and AA adults >16 years (N=1000) in San Diego. During Phase 2 we will offer the COVID-19 vaccine at the participating SYH community health centers and mini-vaccination stations that will be set-up in these communities (only intervention sites) as part of the intervention efforts (i.e., research activities) to increase access and uptake of the COVID-19 vaccine. We have identified various open spaces (e.g., public parks) in these communities to set-up the vaccination stations. SYH is currently offering the vaccine in their facilities as part of their standard of care. It is available to everyone who is eligible according to the state guidelines and does not depend on participating in this study. However, as part of 2VIDA! we will add these mini-vaccination stations to increase access to the vaccine (e.g., open after 5:00pm and on the weekends). Furthermore, data will be collected to assess individual, social, and contextual factors related to access, acceptance, and uptake of the COVID-19 vaccine including: a) sociodemographic characteristics; b) characteristics associated with social marginalization (e.g., homelessness, food insecurity); c) access to and utilization of health care; d) vaccination history, interest, hesitancy and uptake; e) perceptions of the COVID-19 vaccine (e.g., fears, myths, etc.); f) general health; and h) trust in government, research, and social agencies; i) satisfaction with 2VIDA! at baseline and 4-week follow-up. The survey will last approximately 20 minutes and will be self-administered in both English and Spanish. Following the survey participants will be offered the COVID-19 vaccine and the SYH staff will help them set-up an online appointment onsite for the 2nd dose (1 month follow-up) and will be asked to complete a 5 min survey during the follow-up visit. SYH has trained medical staff and a strict protocol for the storage, handling, and application of the vaccine. UCSD staff will not be involved in this process. Furthermore, participants will be asked to provide separate written consent in order to receive the vaccine that will be conducted by SYH staff. Additionally, two focus groups (FGs) will be conducted with members of Latinx and AA communities (n=8-10 participants per group) to obtain feedback on implementation and ways to improve future sustainability and scalability for future vaccination efforts among vulnerable underserved communities. FGs will be transcribed and reviewed for themes specific to 2VIDA! including personal and structural barriers to medical accurate information and the COVID-19 vaccine, benefits, challenges, feasibility, and scalability.

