minutes. SYH will follow strict vaccination protocols (based on the FDA and CDC recommendations and guidelines)^{1,7} and will report all vaccine administration errors, all serious adverse events, cases of Multisystem Inflammatory Syndrome (MIS), and cases of COVID-19 that result in hospitalization or death following administration of the COVID-19 Vaccine to the IRB and to the Vaccine Adverse Event Reporting System (VAERS). Additionally, a detailed protocol has been developed by SYH to handle adverse events related to the COVID-19 vaccine, although none have occurred so far in the application of the COVID-19 vaccine. Staff members have been assigned specific responsibilities (e.g., if warranted, nurses will administer epinephrine or Benadryl and maintain an airway; outreach workers would call 911 and wait for the ambulance). The medical director of the study on behalf of SYH, [name], will be on call at all times, and a licensed nurse will manage all aspects of the COVID-19 vaccination phase. Additionally, project staff, will be responsible for immediately reporting any breaches of protocol, breakdowns in the consent process, violations of confidentiality of the data, complaints by participants or any serious problems or adverse events to the project coordinator who will file an incident report with [name]. [name] will collect any incident reports and communicate serious problems or adverse events to the UCSD HRPP, who will report to NIH if warranted.

Lastly, based on the intervention components and objectives, we do not foresee an increased risk of an individual receiving the 1st dose but not the 2nd dose as a result of participating in this project. The different *2VIDA!* individual and community research activities centered on providing health literacy and addressing vaccine hesitancy, as well as the reminders and tracking mechanisms in place (i.e., providing two additional contacts), we believe that participants from this research projects will be more likely to receive the 2nd dosage.

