16. POTENTIAL BENEFITS

The results of this study will inform local and national scale-up efforts of interventions designed to address vaccine hesitancy and increase access, acceptance, uptake and series completion of the COVID-19 vaccine among Latinx and AA adults in the U.S. Even if the intervention proves ineffective at increasing access, acceptance, uptake, and series completion of the COVID-19 vaccine among Latinx and AA communities, this information is valuable to the development of more effective models in the future and to inform efforts to ending the pandemic. Based on the study design and the nature and severity of COVID-19 infection, the potential knowledge gained from this study outweighs any potential risk and will have an impact on the health of Latinx and AA communities in San Diego that have been severely impacted by the pandemic.

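### As written, the plan lets follow-up measures such as vaccine hesitancy be covariates in the arm comparisons; any comparison adjusted in this way does not estimate the total effect of 2VIDA!

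*SAP*

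**What the plan says.** The covariate sentence is worded identically in the SAP and in Section 8 of the protocol (Data Analysis). Both documents first set out a repeated-measures comparison of the arms. Acceptance and series completion are the primary outcomes, followed by the "secondary outcome variables (increased knowledge of COVID-19 vaccine, increased access to COVID-19 vaccine, vaccine hesitancy". The next sentence reads: "Additional measures at baseline and follow-up will be used as covariates (e.g., outreach and health communication, vaccine hesitancy or mistrust".

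Other parts of the protocol show what kind of variable follow-up hesitancy is:

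- Section 14 (Potential Risks) describes 2VIDA! through its "individual and community research activities centered on providing health literacy and addressing vaccine hesitancy".
- Section 16 (Potential Benefits) says the results will inform the scale-up of "interventions designed to address vaccine hesitancy and increase access, acceptance, uptake and series completion of the COVID-19 vaccine".
- Section 8, Phase II, lists the survey content at baseline and four weeks, including "d) vaccination history, interest, hesitancy and uptake". On the baseline visit it adds: "Following the survey participants will be offered the COVID-19 vaccine".
- Section 5, Aim 1, states the question: "To evaluate the preliminary impact of 2VIDA! compared to the standard-of-care for COVID-19 vaccination services".
- The note on randomisation in Section 5 says of the standard-of-care arm that "no components of 2VIDA! will be deployed".

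**The concern.** Aim 1 asks for the whole effect of offering the programme, by whatever route it works. A covariate measured after the programme has started can carry part of that effect. Hesitancy at four weeks raises two separate problems.

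- **It can lie on the causal path.** If 2VIDA! lowers hesitancy and lower hesitancy raises uptake, holding follow-up hesitancy fixed takes that route out of the estimate.
- **It can follow the outcome.** The vaccine is offered straight after the baseline survey. For people who accept then, hesitancy at four weeks is recorded after acceptance and may be partly a result of it.

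In both cases the adjusted arm difference answers a different question from Aim 1. An analyst who followed the sentence literally could understate a programme that works, overstate it, or report a difference where the total effect is nil.

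**Working it through.** **The plan's own figure.** The only numerical claim is power .90 for an effect size of .20 at alpha .05. The metric, sidedness and attrition rate are not stated. Read as a standardised mean difference, two-sided and ignoring clinics, n per arm = 2(1.960 + 1.282)² / .20² = 526. With 500 per arm and no attrition, .20/√(2/500) = 3.162, and power = Φ(3.162 − 1.960) = .885. This is close to .90 before any attrition. The present point does not depend on it; .20 SD serves below only as a reference effect.

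**What adjustment does.** In a least-squares model with arm and follow-up hesitancy,

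adjusted difference = unadjusted difference − b × D,

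where D is the arm difference in follow-up hesitancy (2VIDA! minus control) and b is the within-arm slope of the outcome on hesitancy. This is an algebraic identity. It holds whether hesitancy comes before or after vaccination, and also for a yes/no outcome fitted by least squares. In SD units b is the within-arm correlation r, so the adjusted effect is .20 − r × D.

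**Illustration.** The documents give neither r nor D, so every value of them is assumed. For r = −.30 and D = −.2: .20 − (−.30)(−.2) = .20 − .06 = .14.

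| Arm difference in hesitancy | r = −.15 | r = −.30 | r = −.50 |
|---|---|---|---|
| fall of .2 SD | .17 | .14 | .10 |
| fall of .3 SD | .155 | .11 | .05 |
| rise of .2 SD | .23 | .26 | .30 |

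Between .03/.20 = 15% and .15/.20 = 75% of the effect is removed, or between .03/.20 = 15% and .10/.20 = 50% is added. With no total effect, a fall of .2 SD gives −.03, −.06 or −.10 SD.

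**With baseline hesitancy also in the model.** The sentence names measures at both times, so the table describes a simpler model than the one it permits. Suppose baseline hesitancy is balanced by arm, correlates with the outcome as strongly as follow-up hesitancy does, and correlates rho with it. The slope on follow-up hesitancy is then (r − rho × r)/(1 − rho²) = r/(1 + rho). For assumed rho of .5 to .8:

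- The 75% removal becomes 75/1.5 = 50% to 75/1.8 = 42%.
- The 15% removal becomes 15/1.5 = 10% to 15/1.8 = 8%.
- The 50% addition becomes 50/1.5 = 33% to 50/1.8 = 28%.

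The distortion is smaller but still there.

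**Is the adjusted figure at least a clean direct effect?** Not in general. Take an assumed model in which 2VIDA! lowers hesitancy by .25, hesitancy has slope −.40 on the outcome, and the direct effect is .10. The total is .10 + .40 × .25 = .20. Adjusting for hesitancy gives .10. Now let an unmeasured factor with coefficient h lower hesitancy and raise the outcome. The slope becomes −.40 − h²/(1 + h²). For h = .3 it is −.483, and the adjusted value is .20 − .483 × .25 = .08. For h = .5 it is −.60, and the adjusted value is .05. The adjusted value is then neither the total effect nor the direct effect.

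**Outreach and health communication.** The term is not defined. If it means outreach received, the same objection applies, because outreach is a Phase I component of 2VIDA! that control sites do not get. If it means something recorded at baseline, such as usual sources of health information, it does not.

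**The case against.** The best defence is that the authors meant less than they wrote. The descriptive paragraph speaks of possible covariates at baseline. The only explicit selection rule, p < .20, stands under the heading on baseline differences. That rule leads to adjusted outcome analyses, which suggests unadjusted ones as well. Aim 2 says intervention effects will be assessed from vaccination and completion rates in the two groups and mentions no covariates. Aim 1 itself calls the evaluation preliminary.

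Part of this stands: the intent is unclear, and one cannot say that every comparison will be adjusted in this way. But none of these passages withdraws the covariate sentence. Neither document limits covariates to baseline, names an unadjusted or baseline-only analysis as primary, or reserves follow-up measures for a mediation analysis. A repeated-measures design does use follow-up values of the outcomes, but this sentence makes additional follow-up measures covariates. A preliminary evaluation still needs the right contrast.

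A reader might infer that the trial's effect estimates will all be biased, by up to 75% and towards no effect. The documents do not support that. They do not say which covariate enters which model, the percentages rest on assumed inputs, and the direction is open. Nor does this point require changes to the p < .20 rule, the list of demographic variables or the planned paired t-tests; those are separate questions.

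**Conclusion.** The concern holds in conditional form. The sentence as written permits follow-up hesitancy or mistrust as a covariate, and any comparison on acceptance or series completion that uses it does not estimate the total effect in Aim 1. That conclusion rests on the wording, the timing of the surveys and the stated purpose of 2VIDA!, not on the illustrative figures. Its practical size depends on how far 2VIDA! moves hesitancy, how strongly hesitancy tracks the outcome, and which models include it. If 2VIDA! left the follow-up covariates unchanged, adjustment would take nothing away from its effect, but the protocol expects a change in hesitancy. The outreach part holds only if the term means outreach received.

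**What to change.** In the SAP and in Section 8 of the protocol, replace the covariate sentence with:

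*Covariates in the arm comparisons on primary and secondary outcomes will be limited to measures taken at baseline (e.g., baseline vaccine hesitancy or mistrust); no measure taken at follow-up will be used as a covariate. Analyses that use follow-up hesitancy, mistrust or outreach received will be reported separately as exploratory.*

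The planned baseline-to-follow-up analysis of each outcome stays, including hesitancy as a secondary outcome. The change is to wording only and needs no new data. The cost is that follow-up measures are no longer available as covariates in the main comparisons; baseline attitude scores remain available for precision.
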